### ***B2d. Tobacco Products***

For Study 1, usual brand of ST products will be used. We chose products that had substantial market share and showed a range in nicotine level and in NNK and NNN levels [4, 46, 75, 151]. Table 2 shows the brands that were chosen for testing. Free/unprotonated nicotine levels were considered high (H) if they were > 5 mg/g, medium (M) if they were between 2-5 mg/g and low if they were < 2 mg/g [3]. TSNA levels were based on a classification that was developed by [name] ([name], report for WHO, TobReg). High (H) levels were NNN plus NNK > than 10 µg/g, Medium (M) levels were NNN plus NNK from 2-10 µg/g, and Low (L) levels were NNN plus NNK < 2 µg/g. Products that are in the Low range for both nicotine and TSNAs tend not be manufactured.

Table 2

Group	Product	Test Date	# Tins/ Regions	Nicotine (mg/g wet)	NNK+NNN (µg/g wet)	Nicotine Group	TSNA Group
1	Camel Snus (All Flavors)	Fall 2010		2.65		Low	Low
	Marlboro Snus (All Flavors)						
	Skoal Long Cut Mint	Fall 2011	3 / 2	1.2	1.23		
	Skoal Fine Cut Original	Spring 2011	1 / 1	2.79	1.88		
2	Copenhagen Long Cut Original	Fall 2010	1 / 1	3.51	2.55	Med	Med
	Kodiak Wintergreen	Spring 2010	9 / 3	4.51	2.73		
	Skoal Bandits Wintergreen	Spring 2010	11 / 3	3.05	3.72		
	Skoal Pouches Straight	Spring 2011	1 / 1	4.02	2.58		
	Skoal Pouches Wintergreen	Spring 2011	1 / 1	3.89	2.81		
	Grizzly Long Cut Straight	Spring 2010	5 / 2	4.23	3.84		
	Skoal Long Cut Straight	Spring 2010	9 / 3	3.15	3.11		
3	Grizzly Long Cut Mint	2010 summary		7.58	3.72	High	Med
	Grizzly Long Cut Wintergreen	Spring 2010	4 / 2	5.12	3.05		
	Grizzly Pouches Wintergreen	Spring 2011	1 / 1	6.25	3.71		
	Skoal Pouches Mint	Spring 2011	1 / 1	5.19	2.15		
	Kodiak Pouches Wintergreen	Spring 2011	1 / 1	5.88	3.44		
4	Grizzly Fine Cut Regular	Spring 2011	1 / 1	4.41	15.3	Med	High
6	Kodiak Long Cut Mint	Spring 2011	1 / 1	3.9	1.91	Med	Low
	Kodiak Long Cut Straight	Spring 2011	1 / 1	4.06	1.88		
8	Copenhagen Fine Cut Original	Spring 2010	9 / 3	2.43	3.45	Low	Med
	Copenhagen Long Cut Straight	2010 summary		2.56	2.07		
	Grizzly Pouches Straight	Spring 2011	1 / 1	0.48	4.0		
	Skoal Long Cut Classic	Spring 2011	1 / 1	2.88	2.88		
	Skoal Long Cut Wintergreen	Spring 2011	1 / 1	2.7	2.51		

Nicotine Group	mg/g wet weight
Low	<3
Medium	3-5
High	>5

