Pearson or Spearman correlations will assess the relationship between toxicant and nicotine exposure and the level of toxicants in the tobacco products. Furthermore, regression models will determine the degree of association between exposure and patterns of use, while controlling for the different ST brands. Specifically, total nicotine equivalents will be correlated with the free nicotine levels of the products and patterns of use; NNAL will be correlated with the NNK levels of the product and patterns of use; NNN exposure will be correlated with the amount of NNN in the product and patterns of use; and 1-HOP exposure will be correlated with the amount of pyrene and patterns of use.

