## **C2. Power Considerations:**

The goal is to enroll 100 subjects for each of the six brands listed in Table 2. The mean toxicant uptake level is expected to vary between brands; however, the standard deviation (SD) should

be similar for all brands. This is the common SD and is equivalent to the root of the Mean Square Error (MSE) from the one-way ANOVA. With a total of 600 subjects, this F-test will have 92% power to detect a significant difference at the 0.05 level if the brands with the largest and smallest means differ by at least one-half the common SD. Therefore, if the common SD for the biomarker was 10 units, then there would be a 92% chance that we find a significant difference between brands if the biggest and smallest means were at least 5 units apart. This analysis was done using Power Analysis and Sample Size (PASS) 2005 by NCSS, Inc.

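### Aim 2's overall NNK and NNN correlations, above all raw-scale Pearson, can be driven by the single Group 4 product; fix the scale and report each with and without Group 4

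*Combined protocol and SAP*

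**What the plan says.** Section C1, Primary Aim 2, states: "Pearson or Spearman correlations will assess the relationship between toxicant and nicotine exposure and the level of toxicants in the tobacco products". The pairs are named: "NNAL will be correlated with the NNK levels of the product and patterns of use", and "NNN exposure will be correlated with the amount of NNN in the product and patterns of use". The choice between the two coefficients is left open. Under Aim 1 the plan expects many biomarkers to need a natural-log scale, but it gives no scale for the product level. It has no influence check and no analysis without any one group.

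Table 2 in section B2d has one product in Group 4, the only one classed High for TSNA: "Grizzly Fine Cut Regular Spring 2011 1 / 1 4.41 15.3" (tins/regions, nicotine, NNK+NNN). The next highest NNK+NNN value is 4.0 ("Grizzly Pouches Straight Spring 2011 1 / 1 0.48 4.0"). The lowest printed value is 1.23 ("Skoal Long Cut Mint Fall 2011 3 / 2 1.2 1.23"). No value is printed for Camel or Marlboro Snus. Section C2 sets the group sizes: "The goal is to enroll 100 subjects for each of the six brands listed in Table 2". Section B2c says that product constituents will be measured in tins collected from 10 subjects per brand per site, so the analysis need not use the Table 2 figures.

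**The concern.** Nothing in Table 2 lies between 4.0 and 15.3 µg/g. With one group far out on the horizontal axis, a linear correlation is close to a two-sample comparison of that group with everyone else. Any other feature of that product or its users that raises NNAL or urinary NNN would then appear as a relation with TSNA level. A real gradient among the other products would carry little weight.

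Aim 2 is a primary aim, in a study motivated by toxicant standards for smokeless tobacco. A reader would take a significant coefficient to mean that lower product TSNA goes with lower exposure across the market. That reading needs evidence from more than one product.

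**Working it through.** **The plan's own figure.** The only power figure is for the Aim 1 ANOVA: 92% with six groups of 100 and a range of means of 0.5 SD. Six equally spaced means have squared deviations summing to 2 × (0.25² + 0.15² + 0.05²) = 0.175 SD², so the noncentrality is 100 × 0.175 = 17.5 and the power is 91.6%. This matches. No figure is given for the Aim 2 correlations.

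**Inputs.** Group means of NNK+NNN from Table 2, users spread evenly over the products with a value (assumption): Group 1, 1.555; Group 2, 2.878; Group 3, 3.289; Group 4, 15.3; Group 6, 1.895; Group 8, 2.982. NNK+NNN stands in for NNK and NNN separately (assumption).

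**Share of the variation in product level that is Group 4 versus the rest.** Share = p(1 − p)D² / total variance, where p = 100/600 and D is Group 4 minus the mean of the others.

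- Raw: the mean of the others is 2.520, so D = 12.780. Numerator: 0.1389 × 163.34 = 22.69. Total variance: 4.820² = 23.24. Share: 97.6%.
- Log: D = 2.728 − 0.869 = 1.859. Numerator: 0.1389 × 3.455 = 0.480. Total: 0.758² = 0.575. Share: 83%.
- Ranks: mean ranks are 550.5 and 250.5, so the numerator is 0.1389 × 300² = 12,500. The total is about 30,000 before ties. Share: 42%.

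| Setting | Raw | Log | Ranks |
|---|---|---|---|
| 100 in Group 4; snus omitted, 1.0 or 0.5 µg/g | 96-98% | 66-83% | 42% |
| 20 in Group 4; same snus range | 87-91% | 31-54% | 11% |

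Placing the two Long Cut Straight products in Group 2 or Group 3 makes almost no difference. Without Group 4 the SD of product level falls from 4.82 to 0.81 µg/g.

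**A rise confined to Group 4.** Suppose Group 4 users are d SD higher for some non-TSNA reason and there is no gradient elsewhere. Then r = d × √[p(1 − p)] × √share / √[1 + d²p(1 − p)]. For d = 0.5, r = 0.5 × 0.373 × 0.988 / 1.017 = 0.18. With N = 600, t = 0.181 × √(598 / 0.967) = 4.5. The simulated share of studies significant at 0.05 is about 99% for raw Pearson, 98% for log-level Pearson, 81-83% for Spearman, and 5-6% for Pearson among users outside Group 4. For d = 0.3 the figures are 78%, 70%, 41% and 5%.

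**Can the coefficient tell the two patterns apart?** Simulated log biomarker, residual SD 0.8-1.2 (assumed):

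| Truth | Raw Pearson, all | Spearman, all | Pearson, outside Group 4 |
|---|---|---|---|
| Exposure proportional to level | 0.52-0.66 | 0.47-0.60 | 0.27-0.38 |
| Step in Group 4 only, ln(15.3/2.7) | 0.47-0.62 | 0.29-0.37 | about 0 |
| Gradient outside Group 4 only | 0.08-0.11 | 0.21-0.30 | 0.27-0.38 |

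In the first two rows both overall coefficients are significant in about 100% of runs. In the third, raw Pearson is significant in only 45-76% of runs, although the gradient outside Group 4 is found in about 100%.

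**What the remaining users can show.** By Fisher's z with n = 500, r = 0.125 gives arctanh(0.125) × √497 − 1.96 = 0.84, which is 80% power; r = 0.15 gives 92%. This treats users as independent. They share product levels (21 listed products outside Group 4 have a value), so real precision is lower.

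**The case against.** The strongest reply is that the plan also allows Spearman, where Group 4 carries 42% of the variation and most of it lies among the other products. That stands, so the near-total dominance applies to raw-scale Pearson only. Spearman still rejects in 81-83% of runs when only Group 4 is raised by 0.5 SD, so choosing it does not settle the matter.

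Second, Table 2 gives screening values. They are sums of NNK and NNN, and 15.3 comes from one tin in one region. The analysis will use separate NNK and NNN results from subjects' tins, so the leverage could be smaller or larger. This also stands and makes the sizes conditional. The 0.5 SD shift is illustrative and has no source in the documents.

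Third, Aim 1 reports geometric means with CIs by brand and Tukey comparisons, where a pattern confined to Group 4 would be visible. Aim 3 models constituent levels with user factors and controls site and lifestyle confounders. These help, but neither supplies the missing estimate. The ANOVA estimates no slope on product level, the Aim 2 regressions address patterns of use with brand controlled, and the Aim 3 models include brand terms.

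Fourth, Aim 2 asks only whether exposure is related to constituent levels, and products were chosen to give a range. An extreme product is information. It would be too strict to forbid calling exposure related to TSNA level unless the association survives without Group 4.

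**Conclusion.** The point holds in a conditional form. If tin levels resemble Table 2, with 100 users per group spread evenly over products, raw-scale Pearson is about 96-98% a Group 4 contrast, against 66-83% on the log scale and 42% on ranks. A significant overall coefficient of either kind does not by itself show that exposure rises with TSNA level across products.

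A reader might go further and infer that the study cannot show such a relation. The documents do not support that. Up to 500 other users span 1.23 to 4.0 µg/g, a 3.3-fold range, and under proportional exposure the simulation finds the gradient among them in about 100% of runs (independence assumed). The number may be smaller: Group 6 appears in Table 2 but not in the eligibility list in section B2a, and without it up to 400 remain. The gap is in the planned analysis, not in what the data can show. It matters because a statistic that the plan allows could mislead on a primary aim.

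**What to change.** In section C1, Primary Aim 2, for NNK and NNN:

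1. Enter product level on the log scale against the log biomarker, or name Spearman, in place of leaving raw-scale Pearson open.
2. Report each association with its CI twice, with and without Group 4, and add a plot of biomarker against level marked by product.
3. State in the conclusion whether the relation is also seen among the remaining groups or rests on Group 4.

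Item 2 is essential, because item 1 alone leaves the ambiguity in place. The cost is SAP wording and one extra run per biomarker, with no new data. The CI without Group 4 will be wider, and wider still once the sharing of product levels between users is allowed for.

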### *Secondary Aims*

3. To determine if exposure is also moderated by individual factors such as degree of dependence, nicotine metabolism, age of initiation and duration of use, negative affect and stress, amount of alcohol use and perception of ST harm and environmental and social factors such as use among social network, cost of the product, bans on tobacco use.

Analysis of covariance (ANCOVA) and regression methods will measure the impact of level of tobacco constituents (e.g., free nicotine, NNK, NNN, pyrene), ST Dependency score, nicotine metabolite ratio, age of initiation, duration of use, negative affect and depressed mood (PANAS negative affect score and CESD), stress (Perceived Stress Scale), amount of alcohol use (NIAAA Alcohol Use Questionnaire), perception of ST harm (Perceived Health Risk), social network (percent of social network who uses ST and who smokes), price of product and income, and tobacco bans (smoking and ST bans at work, school or home) on exposure measures (total nicotine equivalents, total NNAL, total NNN). Potential confounding factors such as site and as assessed by the Exposure and Lifestyle measures will be examined and controlled. The ST brand will be included in the model to access the main effects adjusted for product brand and to explore interactions between individual, environmental and social factors and brands on exposure measurements. For example, does a high ST Dependency score increase exposure to toxicants for some brands more than others?

4. To estimate the overall toxicant burden in the population by examining the extent of carcinogen exposure of the products that have the greatest market shares.

The analysis for this aim is an extension of primary aim 1. The market share for each of the six ST products will be represented as the percent of the total. Market share information will be obtained from the Maxwell Report. Using the mean toxicant exposure level for the six brands from the one way ANOVA, a weighted mean value will be calculated across the brands, with the percent of the market as the weight. This will be done for each biomarker. Thus, the more popular brands will have more influence on the overall exposure level.

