## REVISION HISTORY

Version Date	Revision summary	Protocol		Consent		Other	
		Revised	Version Date	Revised	Version Date	Revised?	Version Date
5/25/2009	original to IRB		5/9/2009		11/15/07		11/15/07
10/20/09	Revisions from start-up meeting - eliminate visit 2 ■	Amend ment 1	10-20- 09		10/29/09		
11/25/2009	Final Protocol		12/31/20 09				
4/5/2010	Amendment 1 Increase payment to \$100; change advertisement Revised product list to change Skoal bandits straight to Skoal bandits wintergreen		4/5/2010		3/25/2010		
7/13/11	Updated tobacco product list for eligibility and on page 9		7/13/11	NA			NA

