### **B2. Procedures**

*Subject recruitment.* Subjects (N=600) will be recruited from a) Minneapolis/St. Paul, MN, b) Eugene, OR, and c) Morgantown, WV. Each site will recruit 200 subjects over the course of 2 years, with a total of 100 subjects recruited for each brand that is listed in Table 2. We anticipate no problems with recruitment. Surveys conducted in 2007 or 2006 estimated Minnesota and Oregon male ST prevalence of 6.0% and 6.5%, respectively. The 2006 West Virginia Adult Tobacco Survey estimated the male ST prevalence to be about 16%. Multiple avenues of recruitment will be pursued to ensure as representative of a sample as possible. These methods include radio, cable, newspapers (want ads and display ads), restroom stall ads, sporting good stores, WIC clinics, internet and press releases. The recruitment advertisements will state that daily ST users are needed for a study that examines the effects from ST use; blood (only at U of MN site), oral cells (only at U of MN site) and urine samples will be obtained. It will further state that subjects will be paid for participation. Potential adult subjects will be asked to call the research clinic number where the study will be explained, brief phone screening will be conducted, and interested and potentially eligible subjects will be asked to attend an orientation meeting. The brands of ST will not be listed on the advertisements to ensure that we are recruiting actual users of the brands rather than subjects who falsely claim using one of the brands of interest in order to obtain money for study participation. Subjects will be informed that the study determines the extent of exposure to toxicants and the effects of these exposures across different brands of ST.

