#### ***B2a. Subject inclusion/exclusion criteria***

Adult ST users (18 years or older) who are interested in the study will telephone the research clinics, be informed about the study, and initially screened in order to determine whether they meet specific inclusion/exclusion criteria.

Inclusion criteria include:

- a) use of a consistent brand and daily amount of ST for the past 6 months;
- b) in good physical health (no unstable medical condition and no kidney or liver disease);
- c) stable, good mental health (e.g., no recent unstable or untreated psychiatric diagnosis, including substance abuse, as determined by the DSM-IV criteria).
- d) use of one of the following smokeless tobacco products:

(UPDATED BRANDS BY GROUP): 1) Camel Snus, Marlboro Snus; 2) Skoal Long Cut Mint, Skoal Fine Cut Original, Copenhagen Long Cut Original, Kodiak Wintergreen, Skoal Bandits Wintergreen, Skoal Pouches Straight, Skoal Pouches Wintergreen; 3) Grizzly Long Cut Straight, Skoal Long Cut Straight, Grizzly Long Cut Mint, Grizzly Long Cut Wintergreen, Grizzly Pouches Wintergreen, Skoal Pouches Mint, Kodiak Pouches Wintergreen; 4) Grizzly Fine Cut Regular; 8) Copenhagen Fine Cut Original, Copenhagen Long Cut Straight, Grizzly Pouches Straight, Skoal Long Cut Classic, Skoal Long Cut Wintergreen, and Dual Users of Camel and Marlboro Snus and cigarettes.

Exclusion criteria include:

- a) currently using other tobacco (>1 episode of smoking per week on average; no combustible tobacco use in the last 21 days and CO >8 ppm) or nicotine products;
- b) female subjects pregnant or nursing;
- c) use of alcohol within the last 24 hours of testing and no more than 21 drinks per week at phone screening;
- d) use of any inhalable drugs in the last 14 days and regular use >1 times per week;
- e) current infection or use of antibiotics;
- f) active liver or kidney disease, or UTI which would interfere with biomarker measures.

Subjects meeting these criteria will then be asked to come into the research clinic for an orientation visit, to provide informed consent, and to engage in more thorough screening. Subjects will also be required to complete a tobacco use questionnaire, medical history form (which will be reviewed by a physician), and baseline measurements (see below).

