### **C. Statistical analyses**

#### **C1. Analytic Approach**

##### ***Primary Aims***

1. To determine the toxicant exposure associated with currently marketed oral tobacco products with varying levels of toxicants and nicotine.

Subject characteristics will be examined across sites and ST users at each site will be compared to the characteristics of the respective state population of ST users. The outcomes for this study are the uptake of toxicants, as measured by biomarkers of exposure including NNAL, NNN, nitrosoamino acids,

1-HOP and total nicotine equivalents and biomarkers of effect such as CVD risk factors. The distribution of each biomarker will be examined to determine if a data transformation is necessary. From our previous experience, the distributions of many biomarkers are often skewed with a long right tail and need to be analyzed in the natural log scale. The two biomarker assessments for nicotine from each subject will be used to evaluate the reliability, as measured by the intraclass correlation. The two readings will then be averaged for the subsequent analysis. The geometric mean and the corresponding 95% confidence interval for the biomarkers will be calculated for each brand. The one-way analysis of variance (ANOVA) will be used to compare the mean toxicant levels between all six brands. If this global test is significant, then the Tukey's studentized range procedure will be used for pair-wise comparisons between brands, while maintaining an overall significance level of 5%.

2. To determine if toxicant and nicotine exposure is related to product factors such as the levels of these constituents (nicotine, NNK and NNN) in the products and patterns of use such as tins per week, dips per day, duration per dip, total dip duration (dip per day x duration per dip), weight per dip.

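### Aim 4's market shares act only between six product groups; inside a group, each product counts by how many of its users enrolled

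*Combined protocol and SAP*

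**What the plan says.** Section C1, Secondary Aim 4, gives the estimator: "Using the mean toxicant exposure level for the six brands from the one way ANOVA, a weighted mean value will be calculated across the brands". The weights are percent market shares: "The market share for each of the six ST products will be represented as the percent of the total". Their source is also given: "Market share information will be obtained from the Maxwell Report". The stated purpose is: "Thus, the more popular brands will have more influence on the overall exposure level".

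The means come from Primary Aim 1: "The one-way analysis of variance (ANOVA) will be used to compare the mean toxicant levels between all six brands". Section B2 sets the recruitment target, "with a total of 100 subjects recruited for each brand that is listed in Table 2", and C2 repeats it as 100 for each of six.

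The product lists no longer contain six products. Table 2 in B2d lists 24, under group numbers 1, 2, 3, 4, 6 and 8. B2a presents the eligible products by group as well; one entry reads "8) Copenhagen Fine Cut Original, Copenhagen Long Cut Straight, Grizzly Pouches Straight, Skoal Long Cut Classic, Skoal Long Cut Wintergreen". The Revision History dates the change to 7/13/11: "Updated tobacco product list for eligibility and on page 9". Aim 4 still speaks of six products or brands. No section redefines that unit, sets a quota for a product within a group, or applies a market share within a group.

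**The concern.** Aim 4 describes a mean in which a product's influence rises with its popularity. With six single products, six shares times six means gives that. With six groups, a group's combined share multiplies the plain mean of whoever enrolled in it. A product with a small share but many enrolled users can then dominate its group's mean and carry the whole group's share. Where that happens, the error is a bias that does not shrink as subjects are added. At stake is whether the reported population toxicant burden is the quantity Aim 4 defines.

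**Working it through.** **The plan's own figure.** Aim 4 states no number. The only computed figure for the six units is the 92% power in C2. With six means equally spaced over 0.5 SD and 100 per unit, the squared deviations sum to 2 x (0.25² + 0.15² + 0.05²) = 0.175. The noncentrality is 100 x 0.175 = 17.5 on 5 and 594 df, and power is 91.6%. That figure reproduces and does not bear on the weighting.

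**Counting units.** By row position, Table 2 has 4, 7, 5, 1, 2 and 5 products in Groups 1, 2, 3, 4, 6 and 8: 24 products in six groups. B2a has 2, 7, 7, 1 and 5 in Groups 1, 2, 3, 4 and 8: 22 products in five groups, with no Group 6. The largest group has seven products in either list.

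**The algebra.** For group g with n_j users of product j and product mean m_j:

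- ANOVA group mean = Σ n_j m_j / Σ n_j, so product j has weight n_j / n_g.
- Aim 4 as written = Σ_g S_g x (group mean), where S_g is the group's share.
- The popularity-weighted mean = Σ_g Σ_j s_j m_j, where s_j is the product's own share and Σ_j s_j = S_g.

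The last two agree for any set of product means only if n_j / n_g = s_j / S_g in every group.

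**Can within-group weights matter?** Table 2 NNK+NNN (µg/g wet) is used as a stand-in for exposure:

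| Group | Membership | Range | Ratio | Simple mean |
|---|---|---|---|---|
| 2 | Table 2 | 2.55-3.84 | 1.5 | 3.05 |
| 3 | Table 2 | 2.15-3.72 | 1.7 | 3.21 |
| 8 | both lists | 2.07-4.00 | 1.9 | 2.98 |
| 2 | B2a | 1.23-3.72 | 3.0 | 2.50 |

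**Hand example, Group 8.** Assume equal enrolment, with the lowest product holding 60% of the group's sales and the other four 10% each.

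- Enrolment-weighted: (3.45 + 2.07 + 4.00 + 2.88 + 2.51) / 5 = 2.98.
- Share-weighted: 0.6 x 2.07 + 0.1 x 12.84 = 2.53.
- Group error: 2.982 / 2.526 - 1 = +18%.

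Now carry this to the overall mean. Hold the other groups at their simple means, with Group 1 assumed to be 1.5 because the table gives no snus values.

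- Six equal group shares: (1.5 + 3.049 + 3.214 + 15.3 + 1.895 + 2.982) / 6 = 27.94 / 6 = 4.66, against 27.484 / 6 = 4.58, an error of +1.7%.
- Group 4 at zero share: 12.64 / 5 = 2.53 against 12.184 / 5 = 2.44, an error of +3.7%.

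**Upper case.** Shares and enrolment mixes were drawn independently and uniformly within each group, 200,000 pairs, with error = enrolment-weighted / share-weighted - 1.

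- *Group means, Table 2 membership:* median absolute error 5.5%, 6.8% and 9.0% in Groups 2, 3 and 8. It exceeds 10% in 22%, 34% and 45% of draws.
- *Group 2, B2a membership:* median 9.5%, above 10% in 48% of draws.
- *Overall Aim 4 mean (Table 2 membership, Group 1 fixed at 1.5 with no spread):* median 1.4% with six equal group shares, 1.5% with random group shares, 2.3% with Group 4 at 5%, and 3.1% with Group 4 at 0%. It exceeds 10% in 0-3% of draws.

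**The case against.** The strongest reply is that recruitment works against the bias. B2 seeks a representative sample, keeps brand names out of the advertisements, and enrols people on their usual product with no quota inside a group. Such recruitment may fill a group much as local users choose, and if that matches market share the error is zero. The targets of 100 per unit and 200 per site do not by themselves distort the mix within a group. All of this stands as a reason why the error may be small. It does not ensure that product mix follows share, and nothing in the plan checks it.

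Three stronger readings are tempting, and the documents do not support them.

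- A reader might take the 5-10% group errors as the error in the reported figure. Aim 4 reports one mean across six groups, where the same assumption gives about 1.4-3%. The group-level size is approached only if one affected group holds most of the market, and no shares are given.
- A reader might use Table 2 test dates to infer which products could be recruited throughout, and so derive a direction of bias. No section links test date to eligibility, and the Revision History does not say which products the update added. One product on the list has a Fall 2011 test date, after the 7/13/11 update. No direction can be claimed.
- A reader might treat the Table 2 grouping as settled. B2a places Skoal Long Cut Mint and Skoal Fine Cut Original in Group 2, and the Grizzly and Skoal Long Cut Straight products in Group 3, whereas the table's row positions put them in Groups 1 and 2. Row positions may be an effect of text extraction, but the absence of Group 6 from B2a is in running text.

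The stand-in is also weak. Aim 4 concerns urinary biomarkers, many Table 2 values rest on one tin, and NNK+NNN says nothing about 1-HOP or nicotine.

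**Conclusion.** The defect holds. Read literally, Aim 4 does not produce the mean it describes unless enrolment follows market share within every group. This rests on taking the six units to be Table 2's groups; no section says so outright, but with 24 products listed no other set of six exists.

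The actual error cannot be computed from the documents. The percentages above are upper-case illustrations under the stated assumptions, not estimates for this study. An overall effect of that order, in a descriptive secondary aim, makes this a correction the sponsor should make, not one that threatens the primary aims.

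**What to change.** 1. Reconcile the product list and group membership between B2a and Table 2, including Group 6, before any share is attached.
2. In Aim 4, replace the six products as the weighting unit with the individual enrolled products. Weight each product's mean exposure by its own market share, rescaled to sum to 100% over the products studied.
3. Where a product has few users, or the market report gives no separate share, pool it with the other such products in its group under their combined share. Fix the threshold for few users in advance.
4. Report the six-group version as a sensitivity analysis.

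The cost is SAP wording and a re-weighting of data already collected, since the Tobacco Use History questionnaire records brand used. The confidence interval will be somewhat wider because some products will have few users; by how much cannot be stated without enrolment by product. The method also depends on product-level shares being available in the market report, and the pooling rule covers the case where they are not.

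### Aim 4 estimates population toxicant burden from the Aim 1 ANOVA means; for any log-analysed biomarker these are geometric means, which understate the mean burden

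*Combined protocol and SAP*

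**What the plan says.** All references are to the combined protocol and SAP, section C1.

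Aim 4, under Secondary Aims, sets its target as follows: "To estimate the overall toxicant burden in the population by examining the extent of carcinogen exposure of the products". It ties its method to the primary analysis: "The analysis for this aim is an extension of primary aim 1". The estimator is "Using the mean toxicant exposure level for the six brands from the one way ANOVA, a weighted mean value will be calculated" across brands, "with the percent of the market as the weight". On scope it adds: "This will be done for each biomarker".

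Aim 1, under Primary Aims, makes transformation a decision for each biomarker: "The distribution of each biomarker will be examined to determine if a data transformation is necessary". From past experience it expects many biomarkers to have a long right tail and to "need to be analyzed in the natural log scale". It names one brand-level summary: "The geometric mean and the corresponding 95% confidence interval for the biomarkers will be calculated for each brand".

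Aim 4 does not say on which scale its brand mean is taken, and it gives no step for returning from the log scale.

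**The concern.** A population burden is a total, or equivalently the number of users times the average exposure per user. Only the arithmetic mean has that property. A geometric mean describes a typical user and discounts the long right tail that the plan itself expects, although heavily exposed users contribute most to a total.

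If Aim 4 is followed as an extension of Aim 1, a log-analysed biomarker yields a weighted geometric mean that is reported as a burden. At stake is the absolute level of the Aim 4 estimate, biomarker by biomarker. Logged and unlogged biomarkers would also be summarised by different kinds of mean under one label.

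**Working it through.** **The plan's own figures.** No figure is stated for Aim 4. The only computed figure in section C is the 92% power of the six-brand F-test (C2). It reproduces if the six means are equally spaced over 0.5 SD with 100 subjects each: noncentrality 100 × 2 × (0.25² + 0.15² + 0.05²) = 17.5 on 5 and 594 degrees of freedom, power 91.6%. This has no bearing on Aim 4. C2 works in SD units, and its example SD of 10 units comes without a mean, so neither a coefficient of variation nor a log-scale SD can be derived.

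**Inputs.**
- Estimator: share-weighted brand means from the one-way ANOVA (Aim 4).
- Scale: natural log where judged necessary, expected for many biomarkers (Aim 1).
- Within-brand log-scale SD, s: not given. Assumed range 0.3 to 1.5.
- Market shares: not given. They are not needed for the main result.

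**Direction.** For any positive variable that is not constant, the geometric mean is below the arithmetic mean. This needs no value of s and no lognormality.

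**Size.** Let log exposure in brand i be normal with mean m_i and SD s.
- Geometric mean: exp(m_i).
- Arithmetic mean: exp(m_i + s²/2).
- With weights w_i, the ratio of the Aim 4 result to the weighted arithmetic mean is Σ w_i exp(m_i) / Σ w_i exp(m_i + s²/2) = exp(-s²/2) when s is common to the brands. The weights cancel.
- Shortfall: 1 - exp(-s²/2).

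| Assumed s | Shortfall |
|---|---|
| 0.3 | 4.4% |
| 0.5 | 11.8% |
| 0.8 | 27.4% |
| 1.0 | 39.3% |
| 1.2 | 51.3% |
| 1.5 | 67.5% |
| Untransformed analysis | 0% |

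**Order of operations.** If log means are weighted first and the result is then exponentiated, the shortfall grows slightly. With illustrative shares of 30, 25, 20, 10, 10 and 5% and brand log means spread over 0.5 SD, it is 27.9%, 40.0% and 52.1% at s = 0.8, 1.0 and 1.2.

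**Simulation check.** With s = 1.0, 100 subjects and 2,000 repeats, the true mean is exp(0.5) = 1.649. The raw arithmetic mean averaged 1.644 and the geometric mean 1.003. The latter is a shortfall of 1 - 1.003/1.649 = 39%, as the formula gives.

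**The case against.** The strongest reply is that Aim 4 never says geometric. It says only that the mean comes from the ANOVA, Aim 1 lists the geometric mean as a separate summary, and transformation is decided for each biomarker. On this view the scale is merely unspecified. That is fair as far as it goes, and it limits the point to logged biomarkers. It does not remove the point. Aim 4 calls itself an extension of Aim 1, an ANOVA on logs produces log means, and nothing in the plan leads back to an arithmetic mean. One could also defend a weighted geometric mean as a summary of typical exposure, but then it should carry that name and not be called a burden.

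Four stronger readings are tempting and are not supported.

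1. *The burden is understated by 27 to 51%.* That range needs s between 0.8 and 1.2, and the documents give no s.
2. *Every biomarker is affected.* Aim 1 expects many to be logged, not all.
3. *The relative contributions of brands are distorted.* This needs log-scale SDs that differ by brand. C2 expects similar SDs, without naming the scale. If they are similar on the log scale, exp(s²/2) is a common factor and relative contributions do not change.
4. *Market share must be converted to user share.* If share means unit sales, brands with heavier users count twice. For two brands with equal numbers of users, where one brand's users consume and absorb k times as much, the weighted mean is 2(1 + k²)/(1 + k)² times the true mean: 10/9 = 1.11 at k = 2 and 20/16 = 1.25 at k = 3. That pushes upward and could offset the shortfall; at s = 0.5 and k = 2 the product is 0.882 × 1.11 = 0.98. But the documents do not say whether the market report gives units, revenue or users. Dividing by tins per week would be wrong for revenue without a price adjustment, and would create a bias if the figure were already user share.

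**Conclusion.** The point holds in conditional form. For each biomarker analysed on the log scale, the Aim 4 estimator as written leads to a weighted geometric mean, which does not match the stated target and lies below it. The downward direction of this component is certain wherever exposure varies within a brand.

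The size rests on lognormality, a common s across brands and an assumed s. It runs from about 4% to 68% over s = 0.3 to 1.5, and no narrower range can be justified from the documents. It is zero for untransformed biomarkers. The net error of the final figure also depends on what the market-share weights measure, which is not stated.

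This affects a secondary aim only. The Aim 1 comparisons are untouched.

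**What to change.** In Aim 4, state for each biomarker that the brand value entering the weighted average is one of the following:

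- the arithmetic mean on the measured scale (per mg creatinine for the urinary biomarkers), or
- for logged biomarkers, the log mean retransformed by exp(s²/2) or by a smearing estimator.

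Give a bootstrap confidence interval for the weighted result. Keep geometric means for the Aim 1 comparisons.

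State what the market-share figure measures. Only if it is unit sales, divide each share by that brand's mean tins per week (a use measure already named in Aim 2) and rescale to 100%. Otherwise leave the weights unchanged.

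The cost is SAP wording and a few lines of code; no new data are needed. The real downside is precision. Under lognormality with 100 subjects per brand, the relative standard error of the arithmetic mean is √(exp(s²) - 1)/10, against about s/10 for the geometric mean: 5.3% against 5.0% at s = 0.5, 13.1% against 10.0% at s = 1.0, and 18.0% against 12.0% at s = 1.2.
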